6.1.2 Week 1 Visit (+/- 2 days)

The Week 1 visit will occur one week post Baseline (+/- 2 days):

- ask the open ended “How Do You Feel” question and document answer in the electronic Case Report Form
- if the subject noted any change in well-being since last investigator contact, document details on the Adverse Event eCRF
- record changes in medication usage from the Baseline (Qualifying) visit
- record vital signs (weight, temperature, resting pulse and blood pressure, and respiration rate)
- ask if the subject experienced weakness, lethargy, or difficulty swallowing or breathing
- evaluate for muscle weakness (ocular and the extremities) or difficulty swallowing or breathing (Appendix B)
- using the rating guide provided in Appendix A, record right and left Investigator’s Global Assessment score of Crow’s Feet, both, “at rest” and “on contraction”
- using the same rating guide provided in Appendix A, record right and left Subject’s Self-Assessment score of Crow’s Feet, both, “at rest” and “on contraction”
- take color photographs (see Appendix C for photograph procedure)
- schedule the subject for the next office visit

6.1.3 Week 2 Visit (+/- 3 days)

The Week 2 visit will occur two weeks post Baseline (+/- 3 days).

- ask a non-leading “How Do You Feel” question and document answer in the electronic Case Report Form
- if subject noted any change in well-being since last investigator contact, document details on the Adverse Event eCRF
- record changes in medication usage
- record vital signs (weight, temperature, resting pulse and blood pressure, and respiration rate)
- ask if the subject experienced weakness, lethargy, or difficulty swallowing or breathing

- evaluate for muscle weakness (ocular and the extremities) or difficulty swallowing or breathing (Appendix B)
- record and transmit a 12-lead ECG
- using the rating guide provided in Appendix A, record right and left Investigator's Global Assessment score of Crow's Feet, both, "at rest" and "on contraction"
- using the same rating guide provided in Appendix A, record right and left Subject's Self-Assessment score of Crow's Feet, both, "at rest" and "on contraction"
- take color photographs (see Appendix C for photograph procedure)
- schedule subject for the next office visit

6.1.4 Week 4 Visit (+/- 4 days)

The Week 4 visit will occur 4 weeks post Baseline +/- 4 days.

- ask a non-leading "How Do You Feel" question and document answer in the electronic Case Report Form
- if subject noted any change in well-being since last investigator contact, document details on the Adverse Event Form
- record changes in medication usage
- record vital signs (weight, temperature, resting pulse and blood pressure, and respiration rate)
- ask if the subject experienced weakness, lethargy, or difficulty swallowing or breathing
- evaluate for muscle weakness (ocular and the extremities) or difficulty swallowing or breathing (Appendix B)
- using the rating guide provided in Appendix A, record right and left Investigator's Global Assessment score of Crow's Feet, both, "at rest" and "on contraction"
- using the same rating guide provided in Appendix A, record right and left Subject's Self-Assessment score of Crow's Feet, both, "at rest" and "on contraction"
- take color photographs (see Appendix C for photograph procedure)
- collect non-fasting blood samples for laboratory safety testing
- female subjects of child-bearing potential will be given a urine pregnancy test
- schedule subject for the next office visit

6.1.5 Week 8 Visit (+/- 7 days)

The Week 8 visit will occur 8 weeks post Baseline +/- 7 days.

- ask a non-leading "How Do You Feel" question and document answer in the electronic Case Report Form

- if subject noted any change in well-being since last investigator contact, document details on the Adverse Event Form
- record changes in medication usage
- record vital signs (weight, temperature, resting pulse and blood pressure, and respiration rate)
- using the rating guide provided in Appendix A, record right and left Investigator's Global Assessment score of Crow's Feet, both, "at rest" and "on contraction"
- using the same rating guide provided in Appendix A, record right and left Subject's Self-Assessment score of Crow's Feet, both, "at rest" and "on contraction"
- take color photographs (see Appendix C for photograph procedure)
- schedule subject for the next office visit

6.1.6 Week 12 Visit (+/- 7 days)

The Week 12 visit will occur 12 weeks post Baseline +/- 7 days.

- ask a non-leading "How Do You Feel" question and document answer in the electronic Case Report Form
- if subject noted any change in well-being since last investigator contact, document details on the Adverse Event Form
- record changes in medication usage
- record vital signs (weight, temperature, resting pulse and blood pressure, and respiration rate)
- using the rating guide provided in Appendix A, record right and left Investigator's Global Assessment score of Crow's Feet, both, "at rest" and "on contraction"
- using the same rating guide provided in Appendix A, record right and left Subject's Self-Assessment score of Crow's Feet, both, "at rest" and "on contraction"
- take color photographs (see Appendix C for photograph procedure)
- schedule subject for the next office visit

6.1.7 Week 18 Visit (+/- 7 days)

The Week 18 visit will occur 18 weeks post Baseline +/- 7 days.

- ask a non-leading "How Do You Feel" question and document answer in the electronic Case Report Form
- if subject noted any change in well-being since last investigator contact, document details on the Adverse Event Form
- record changes in medication usage
- record vital signs (weight, temperature, resting pulse and blood pressure, and respiration rate)

- using the rating guide provided in Appendix A, record right and left Investigator's Global Assessment score of Crow's Feet, both, "at rest" and "on contraction"
- using the same rating guide provided in Appendix A, record right and left Subject's Self-Assessment score of Crow's Feet, both, "at rest" and "on contraction"
- take color photographs (see Appendix C for photograph procedure)
- schedule subject for the next office visit

6.1.8 Week 26 Visit (+/- 7 days)

The Week 26 visit will occur 26 weeks post Baseline +/- 7 days.

- ask a non-leading "How Do You Feel" question and document answer in the Case Report Form
- if subject noted any change in well-being since last investigator contact, document details on the Adverse Event Form
- record changes in medication usage
- record vital signs (weight, temperature, resting pulse and blood pressure, and respiration rate)
- using the rating guide provided in Appendix A, record right and left Investigator's Global Assessment score of Crow's Feet, both, "at rest" and "on contraction"
- using the same rating guide provided in Appendix A, record right and left Subject's Self-Assessment score of Crow's Feet, both, "at rest" and "on contraction"
- take color photographs (see Appendix C for photograph procedure)

6.1.9 Study Exit / Early Termination

The scheduled Study Exit is at Week 26. However, if a subject should discontinue prematurely, the following will be performed in addition to the procedures scheduled for the patient's terminating visit:

- collect non-fasting blood samples for laboratory safety testing

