3.4.3 Hematology

Non-fasting clinical hematology evaluations are:

hemoglobin, hematocrit, red blood cell count, white blood cell count, with a differential, and a platelet count.

Non-fasting clinical hematology evaluations will be performed at Week 0 (Baseline), Week 4, and Week 26/End of Study.

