3.4.4 Clinical Chemistry

A standard non-fasting chemistry panel will be performed which will include the following parameters:

glucose, uric acid, calcium, sodium, potassium, phosphorus, chloride, alkaline phosphatase, aspartate aminotransferase, alanine aminotransferase, total bilirubin, bicarbonate, creatinine, blood urea nitrogen, lactate dehydrogenase, total protein, albumin.

The chemistry panel will be performed at Baseline (Week 0), Week 4, and Week 26/End of Study. A urine pregnancy test will be performed for women of child-bearing potential at Baseline and the Week 4 visit.

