3.4.6 Immunogenicity

Plasma samples will be banked for future analysis of anti-botulinum serum antibodies as a safety parameter for possible immunization against botulinum.

[figure not shown]
Samples will be taken at Baseline, Week 4, and Week 26.

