3.5 Study Visits and Procedures

A schematic study diagram is shown below:

Procedure	Scr./BL	W 1	W 2	W 4	W 8	W 12	W 18	W 26	End of Study#
	Day 0 ± 0	Day 7 ± 2	Day 14 ± 3	Day 28 ± 4	Day 56 ± 7	Day 84 ± 7	Day 126 ± 7	Day 182 ± 7	
Informed Consent	X								
Assess Eligibility & Medical History	X								
Review Con-meds	X	X	X	X	X	X	X	X	
Record AEs	X	X	X	X	X	X	X	X	
Weight and Vital Signs	X	X	X	X	X	X	X	X	
Signs of Botulinum Spread	X	X	X	X					
Hematology and Chemistry	X			X					X
Anti-Botulinum Antibodies	X			X					X
Urine Pregnancy test (WOCBP)	X			X					
ECG	X		X						
IGA Score	X	X	X	X	X	X	X	X	
Subject Self-Assessment (SSA)	X	X	X	X	X	X	X	X	
Photography	X	X	X	X	X	X	X	X	
Randomization	X								
Apply Study Medication	X								

also for early termination

The study will consist of up to 8 office visits.

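### Section 6 lists no Week 26 blood draw for subjects who complete the study, although Section 3.4 and the visit schedule require one

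*Combined protocol and SAP*

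**What the plan says.** Section 3.4 sets the sampling times. For hematology (3.4.3): "Non-fasting clinical hematology evaluations will be performed at Week 0 (Baseline), Week 4, and Week 26/End of Study". For chemistry (3.4.4): "The chemistry panel will be performed at Baseline (Week 0), Week 4, and Week 26/End of Study". For the banked antibody plasma (3.4.6): "Samples will be taken at Baseline, Week 4, and Week 26".

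The Section 3.5 schedule has separate rows for "Hematology and Chemistry" and "Anti-Botulinum Antibodies". Each is marked at baseline, Week 4 and in an End of Study column that stands apart from the W 26 column. A footnote extends the End of Study column to early termination.

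Section 6 gives the visit-by-visit procedures. The Week 26 list (6.1.8) closes with "take color photographs (see Appendix C for photograph procedure" and has no blood sample. Section 6.1.9, headed for both study exit and early termination, first places the scheduled exit at Week 26. It then introduces its only listed procedure, a safety blood draw, with "if a subject should discontinue prematurely, the following will be performed in addition to the procedures scheduled". The baseline (6.1.1) and Week 4 (6.1.4) lists include blood for laboratory safety testing but do not name the antibody sample.

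**The concern.** Site staff commonly run visits from the procedure lists. For a completer at Week 26, 6.1.8 has no draw, and 6.1.9 offers one only to subjects who leave early. The W 26 column of the schedule is also blank for both blood rows, because the marks sit one column further on.

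The data at stake are the late safety laboratory values and the last of three antibody time points. A Week 26 sample that is not taken cannot be obtained afterwards. If the draw were made only in early leavers, end-of-study laboratory data would exist for a selected subset and not for the randomized groups.

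**Working it through.** The plan gives no figure to reproduce here. The check sets the passages side by side and then counts samples.

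| Time point | Section 3.4 | Schedule (3.5) | Section 6 |
|---|---|---|---|
| Baseline | hematology, chemistry, antibody | both rows marked | 6.1.1: safety blood; antibody not named |
| Week 4 | hematology, chemistry, antibody | both rows marked | 6.1.4: safety blood; antibody not named |
| Week 26, completer | hematology, chemistry, antibody | both rows marked under End of Study | 6.1.8: no blood; 6.1.9: draw only on premature discontinuation |
| Early termination | hematology and chemistry at End of Study | both rows marked, through the footnote | 6.1.9: safety blood; antibody not named |

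**Does the End of Study column cover completers?** Yes. Its footnote adds early termination to the column's scope, so the column's first meaning is the scheduled end. Sections 3.4.3 and 3.4.4 join Week 26 and End of Study as one time point, and 3.4.6 names Week 26 outright.

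**Can a completer reach the draw through Section 6?** Not as written. Section 6.1.8 has no blood item. In 6.1.9 the sentence that places the exit at Week 26 lists no procedures, and the sentence that lists the draw is conditional on leaving early.

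**Is Section 6 only a summary, so that a missing line means nothing?** It does not read that way. It itemizes the ECG at baseline and Week 2, the pregnancy test at baseline and Week 4, and the safety draw at baseline and Week 4, all in agreement with the schedule. In a list that is otherwise complete on these tests, a missing line can be read as not required.

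**Size.**
- Panels planned per completer: 3 (baseline, Week 4, end of study), so 3 − 1 = 2 are post-baseline.
- Panels listed in Section 6 per completer: 2, so 2 − 1 = 1 is post-baseline. The unlisted panel is half of the post-baseline laboratory data.
- Across the study, with N = 72 (Section 3.2) and no dropout: 72 × 3 = 216 panels planned and 72 × 2 = 144 listed, a difference of 72.
- Completers with no end-of-study draw listed = 72 × (1 − d), where d is the dropout fraction. The documents give no value for d. At d = 0 this is 72; at d = 0.20 it is 57.6, or about 58. The range 0 to 0.20 is an assumption for illustration.

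**What does not depend on these samples?** The efficacy analyses in 9.2.2 and 9.2.3 use wrinkle scores only. The cohort safety review follows Week 4 (3.1), and 6.1.4 lists that draw. Section 9.2.4 rests safety mainly on adverse event frequency and plans no inferential safety tests. Section 9 specifies no antibody analysis.

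**The case against.** The strongest reply is that the plan already requires the samples. Three parts of Section 3.4 and the schedule say so, and Section 7.1 requires compliance with the whole protocol. Section 6 nowhere tells a site not to draw blood. The schedule puts the draw under End of Study, whose counterpart is 6.1.9 and not 6.1.8, so the Week 26 list agrees with the W 26 column. The 6.1.9 heading covers study exit, which suggests that completers were meant to be included. On this view the defect is one badly built sentence.

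Much of this stands. The samples could be lost but need not be, and 6.1.9 is the main place to repair. The contradiction remains, because the sentence that should carry the end-of-study draw restricts it to a group narrower than the one Section 3.4 and the schedule specify.

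A reader might go further and infer that no antibody samples would be banked at any visit, because Section 6 never names them. The documents do not support that. Section 3.4.6 sits under the safety parameters and describes "anti-botulinum serum antibodies as a safety parameter", so the general phrase for safety laboratory blood can be read to include them at baseline, Week 4 and early termination. Section 6 does not name hematology or chemistry either. The opposite reading is also possible, since the plasma is banked for later and has its own schedule row. The phrase is therefore ambiguous at those visits. For completers at Week 26 the ambiguity does not help, because no draw of any kind is listed.

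**Conclusion.** Section 6 is wrong as written on end-of-study blood sampling for completers, and it conflicts with 3.4.3, 3.4.4, 3.4.6 and the schedule. The exposure is one of two post-baseline laboratory panels and one of three antibody samples per completer.

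The counts in the working are a worst case. They assume that every site works from Section 6 alone, and nothing in the documents says that sites would. It would be wrong to conclude that these data will be lost, or that all 72 subjects would lack antibody samples at all three time points. It would also go beyond the documents to call early leavers a minority of known size, since no dropout rate is given.

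The effect is confined to late safety and immunogenicity data. No efficacy result, alpha level or dose-escalation step depends on it. It still merits correction, because a missed sample is irrecoverable and the repair is small.

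**What to change.** Reconcile Section 6 with 3.4 and 3.5:

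- In 6.1.8 and 6.1.9, state that the end-of-study blood draw applies at the scheduled Week 26 exit as well as at early termination, and that it covers hematology, chemistry and the anti-botulinum antibody sample.
- As a secondary clarification, name the antibody sample beside the safety laboratory blood in 6.1.1 and 6.1.4, so that its inclusion does not depend on how the general phrase is read.
- Optionally, note in the 3.5 schedule that for completers the End of Study column is carried out at the Week 26 visit.

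The cost is protocol wording. All of these samples are already planned in 3.4 and 3.5, so no procedure or visit is added, and the sample size and analyses do not change.

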6.1.10 Unscheduled Visits

The subject may contact the investigator or may be called in for additional unscheduled visits due to safety reasons or at the discretion of the investigator or Sponsor. All unscheduled visits will describe the reason for the visit in the electronic Case Report Form. Some of the procedures that may be completed at an Unscheduled Study Visit are as follows:

- Review of adverse events and concomitant medications
- Vital signs
- Collection of blood samples for laboratory safety testing
- Urine pregnancy testing

7 STUDY DURATION AND CONDUCT

7.1 Conduct of Study

This study will be conducted in compliance with the protocol approved by the Institutional Review Board and according to Good Clinical Practice standards. No intentional deviation from the protocol will be implemented without the prior review and approval of the IRB except where it may be necessary to eliminate an immediate hazard to a research subject. In such case, the deviation will be reported to the IRB as soon as possible.

7.2 Duration of Study

Subject enrollment will take approximately one month. The total study duration will be approximately 7-8 months.

Each subject will participate for up to 26 weeks. There will be a (Qualifying) Baseline Visit on Week 0 and seven in-office visits at Week 1, 2, 4, 8, 12, 18, and 26.

7.3 Stopping Rules

The study is designed as a sequential, overlapping cohort, dose-escalation trial. Enrollment will be halted after each cohort until a safety review has been completed.

- Enrollment will be halted in the event that one serious adverse event (SAE), considered to be probably or definitely related to the administration of study medication, is observed.
- Enrollment will be halted in the event that one AE is observed considered to be indicative of distant spread of study medication or unintended exposure to other beings.
- The Sponsor may stop the study in its entirety or discontinue individual study centers at its discretion for any reason or, e.g. if it is observed that the protocol or sound clinical practices are not being followed, or for any other reasons.

The study protocol calls for only one single application of study medication at Baseline (Week 0). Since there is no continuous treatment, no stopping rules for subjects are

applicable and subjects will be encouraged to participate in the study until the scheduled termination visit at Week 26.

7.4 Monitoring for subject compliance

In this study, a single application of study medication at Day 0 is planned. The study medication will be applied by the Investigator or a designated healthcare professional thereby ensuring compliance with the study application procedure.

Subjects will be queried with regards to concomitant medication at all study visits.

8 ADVERSE EVENT REPORTING

Adverse event reporting will be handled in accordance with the IRB requirements and the requirements of other regulatory authorities that may apply, e.g. the Food and Drug Administration.

Adverse Events reporting will be solicited by non-leading "How Do You Feel" questions. Subtle symptoms of local or systemic spread of toxin effect would be unlikely to be recognized by the subjects as related to treatment. Therefore, study participants will be asked if they experienced weakness, lethargy, or difficulty swallowing or breathing. In addition, information derived from change in concomitant medications, laboratory analyses, and clinical observations will be evaluated for possible indications for side effects. Adverse events resulting from concurrent illnesses or reactions to concurrent medications will also be recorded. The Investigator must monitor the condition of the subject throughout the study from the time of obtaining informed consent until the final study visit.

Any adverse event, including both observed and volunteered problems, complaints, and symptoms, will be recorded on the Adverse Event pages of the electronic Case Report Form. When an adverse event occurs, the following information and assessments should be recorded in the adverse event section of the eCRF:

- The signs, symptoms or diagnosis or the event,
- The date and time of onset of the event using the 24-hour clock where midnight is 00:00 and noon is 12:00. Onset is the date when the first sign or symptoms were first noted.
- Date of recovery/ resolution
- The adverse event severity/ intensity using the criteria outlined in Section 8.1.2
- The relationship of the event to the study drug as outlined in Section 8.1.1

- Any other actions required such as therapy, medication, treatment or diagnostic procedure
- Seriousness of the event using the criteria outlined in Section 8.1.3
- Outcome (recovered, recovered with sequelae, not yet recovered, death)

Follow-up of a subject should be conducted until resolution of the adverse event or until the medical condition is stable. The investigator is responsible for the appropriate medical management of all adverse events.

Adverse events will be analyzed and reported after unblinding of the treatment code within the clinical study report. Serious Adverse Events (SAEs) will be reported by the Sponsor within 10 working days to the IRB as well as the regulatory agency, FDA. In addition, any unanticipated problems involving risk to subjects or others, which in the opinion of the local investigator was unanticipated, serious AND at least possibly related to the research procedures will be reported by the Sponsor to the IRB within 10 working days.

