3.4.2 Muscle Weakness or Paralysis

Participants will be monitored for potential signs of *botulinum* induced muscle weakness or paralysis. Subjects will be evaluated for Signs of Botulinum Toxin Spread (muscle weakness - ocular and the extremities) or difficulty swallowing or breathing (cranial nerve assessment, Appendix B).

The neurologic assessments are made at Baseline, Week 1, 2, and Week 4.

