6 STUDY PROCEDURES

6.1.1 Baseline (Qualifying) Visit

Prior to participating in any aspect of the study, each subject will be fully informed, both verbally and in writing, of the conduct and consequences of the study. Each subject must

sign the written Informed Consent prior to the conduct of the Baseline (Qualifying) evaluation.

The investigator will assign a unique identification code to each subject being evaluated for participation in the trial. The following procedures will be conducted:

- using the rating guide provided in Appendix A, record right and left Investigator's Global Assessment score of Crow's Feet, both, "at rest" and "on contraction"
- using the same rating guide provided in Appendix A, record right and left Subject's Self-Assessment score of Crow's Feet, both, "at rest" and "on contraction"
- record medical history and concomitant diseases
- record concomitant medication usage
- record history of botulinum use
- female subjects of child-bearing potential will be given a urine pregnancy test
- assess eligibility according to the Inclusion and Exclusion criteria in 5.1 and 5.2

If the subject is deemed eligible to participate in the study, the subject will be randomized and treated.

- record vital signs (weight, height, temperature, resting pulse and blood pressure, and respiration rate)
- collect non-fasting blood samples for laboratory safety testing
- record and transmit a 12-lead ECG
- take color photographs (see Appendix C for photograph procedure)
- evaluate for muscle weakness (ocular and the extremities) or difficulty swallowing or breathing (Signs of Botulinum Toxin Spread, Appendix B)
- provide the study medication with the lowest available Kit No. to the investigator.
- apply skin-preconditioning using the Dermalroller
- Investigator will apply the topical treatment to the left and right lateral canthal areas
- record subject's experience with the application process
- evaluate for topical adverse event reactions 30 minutes after application using the Irritation Score in Appendix D
- instruct the subject to avoid sun exposure or tanning beds for two days after treatment
- instruct the subject to avoid strenuous activities on the day of application which will cause them to perspire
- instruct the participant not to touch or let others touch the treatment area until the treatment area is washed with soap and water

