Appendix B: Signs of Botulinum Toxin Spread

1. Ask the subject to follow the examiner's finger with his or her eyes without moving his or her head. At eye level, the examiner should move his or her finger to the right of the subject's head and then to the left. Repeat this horizontal motion at the level of the subject's forehead and chin. Note whether there is any abnormality in the form of any inability of the subject's eyes to follow the finger.
2. Ask the subject to raise his/her eyelids. Observe any indication for "drooping".
3. Ask the subject to swallow and note any difficulty doing so.
4. Ask the subject to partially flex his or her arms at the elbow, with fist at shoulder level. Ask the subject to attempt to fully flex his or her arms against the resistance of the examiner pulling on the subject's forearms. Note whether there is an abnormality in the form of any muscular weakness.
5. Ask the subject to squat down and stand up again. Watch for any abnormalities or signs of weakness.

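### The targeted toxin-spread question names no eye symptom, so mild dry eye or visual symptoms could go unrecorded before the Week 4 safety review

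*Combined protocol and SAP*

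**What the plan says.** Section 8 relies first on a non-leading question about how the subject feels. It then explains why that is not enough for this product: "Subtle symptoms of local or systemic spread of toxin effect would be unlikely to be recognized by the subjects as related to treatment". The consequence follows directly: "Therefore, study participants will be asked if they experienced weakness, lethargy, or difficulty swallowing or breathing".

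The Week 1 list (6.1.2) carries the prompt as "ask if the subject experienced weakness, lethargy, or difficulty swallowing or breathing", and the Week 2 and Week 4 lists (6.1.3, 6.1.4) repeat it. The Baseline list (6.1.1) does not include it, but does include the examination: "evaluate for muscle weakness (ocular and the extremities) or difficulty swallowing or breathing (Signs of Botulinum Toxin Spread, Appendix B". Section 3.4.2 gives the timing of that examination: "The neurologic assessments are made at Baseline, Week 1, 2, and Week 4".

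Appendix B has five items, two of them in the eye area. One is finger-following: "Note whether there is any abnormality in the form of any inability of the subject's eyes to follow the finger". The other is lid droop: "Ask the subject to raise his/her eyelids", with the examiner watching for drooping.

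Section 8 also keeps a general rule: "Any adverse event, including both observed and volunteered problems, complaints, and symptoms, will be recorded" on the adverse event pages. Sections 5.3 and 7.4 add a record of all prescription and over-the-counter products and a medication query at every visit.

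**The concern.** The reason given in section 8 covers local as well as systemic spread. The prompts that follow from it suit distant or general effects better than effects at the nearest organ. Elsewhere the protocol takes the eye seriously: present or past dry eye is an exclusion (5.2), the eyes are covered and run-off is directed away from them (4.2), and application inside the orbital rim is forbidden (4.2). After application, no scheduled item asks the subject about the eye.

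What is at stake is the completeness of the safety record at one decision point. Cohort 1 must pass Week 4 and a safety review before the next dose group opens (3.1). Safety rests mainly on adverse event frequency (9.2.4). Section 4.1 chooses a lower starting dose in case the new device raises bio-availability.

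**Working it through.** The plan states no figure on this point and no rate from which one could be computed. The check is therefore a comparison of texts: for each symptom, is there a scheduled question or test that would bring it out?

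**Inputs**
- Targeted question (section 8; 6.1.2 to 6.1.4): weakness, lethargy, difficulty swallowing, difficulty breathing. That is 4 symptoms, of which 0 are specific to the eye.
- Appendix B: eye tracking, lid droop, swallowing, arm flexion against resistance, squat. That is 5 items: 2 in the eye area, both motor signs, and 0 on dryness or on what the subject sees.
- Appendix D: grades skin responses, scored 30 minutes after application (6.1.1). It has no eye item.
- Schedule in 3.5 and visit lists in section 6: no tear test and no visual acuity test at any visit.

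**Coverage by symptom, Weeks 1, 2 and 4**

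| Symptom | Asked directly | Examined |
|---|---|---|
| Lid droop | No | Yes, Appendix B |
| Double vision | No | Motor sign only, by finger-following |
| Blurred vision | No | No |
| Dry or irritated eye | No | No |

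The visit lists from Week 8 onward carry neither the targeted question nor Appendix B; the open question, medication changes and vital signs continue there.

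**What the remaining routes can reach**
1. The open question reaches a symptom if the subject chooses to mention it.
2. The medication review reaches it if the subject uses and reports a product, such as eye drops.
3. Observation by staff reaches it if there is a visible sign. The investigator grades both canthal areas and photographs are taken at every visit, so redness or lid changes have a fair chance of being noticed; dryness or blur without a visible sign does not.
4. Unscheduled visits (6.1.10) reach symptoms that lead to contact with the site.

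A symptom is lost only if it escapes all four. That describes a mild symptom, and section 8.1.2 defines mild as hardly perceptible to the subject and without effect on daily life. This is the kind least likely to be volunteered.

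**The case against.** Four arguments on the other side carry weight.

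**Recording does not depend on attribution.** Section 8 worries that subjects will not link symptoms to treatment, but 8.1 requires every event to be recorded whatever its relationship to the drug, and the visits ask about any change in well-being. A subject who mentions a dry eye is captured even if she blames the weather. This stands, and it narrows the gap to symptoms that are not mentioned at all.

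**The eye is not ignored.** Weakness in the prompt is not tied to a body part, ocular weakness is examined, and at every visit the subject grades her own lines in a mirror in front of staff, having been selected for adequate vision without eyeglasses. This also stands in part. The mirror task is not a vision test and says nothing about dryness.

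**The protocol does not name visual symptoms as a hazard.** Blurred and double vision appear nowhere. The remark in section 1 about the eyes and lachrymal glands describes a drawback of injections. Section 4.1 reports that up to 2,000 U under occlusion was well tolerated and that up to 1,150 U with microneedles was applied safely; Cohort 1 starts at 690 U. This argues for low severity. It does not explain why a question justified by local spread leaves out the adjacent organ.

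**Prompting adds noise.** Rolling along the orbital rim and 10 to 15 minutes of rubbing per side may irritate the eye in any arm. This stands as the main cost of the change.

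A reader might also try to size the problem from the cohort: with 0 eye reports among 24 subjects on 690 U, the one-sided 95% upper limit is 1 − 0.05^(1/24) = 11.7%. That figure depends only on the number of subjects and would be the same after the question is amended. It describes sample size, not symptom capture, and does not measure this gap.

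**Conclusion.** The point holds in a limited form. The targeted question follows from a concern about local and systemic spread, names no eye symptom, and is supplemented in the eye area only by two motor signs. No scheduled item asks about dry eye, blurred vision or double vision. The possible loss is confined to mild symptoms that are not volunteered, not treated with a recorded product and not seen by staff before the Week 4 review. Severity is low; the case for acting is that the remedy costs little.

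The size of the loss cannot be derived, because the documents give neither a rate of eye events nor the share that open questioning would capture.

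Two stronger readings are tempting and unsupported. A reader might infer that the gap could let escalation to 1,100 U go ahead wrongly. Section 7.3 halts enrollment for a related serious event or for signs of distant spread or exposure of others; it sets no threshold for local eye events, so no changed decision can be shown. A reader might also infer that the 12 vehicle subjects in Cohort 1 would give the review a background rate for comparison. The documents do not promise data by arm at that review: subjects and investigators are blinded (3.6), and section 8 places the analysis of adverse events after unblinding, in the study report.

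The conclusion rests on the public text alone. The Investigator Brochure cited in 8.1 is not part of it and might list expected eye events.

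**What to change.** Add *dry or irritated eye, blurred vision or double vision* to the targeted question in section 8 and in the Week 1, 2 and 4 lists (6.1.2 to 6.1.4). Ask the same items before application at Baseline (6.1.1), so that new symptoms can be told from existing ones. Record new positive answers on the adverse event eCRF.

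The cost is a few words in an existing question at three existing visits, plus one short question at Baseline, with no new visit, test or staff. The downside is some additional mild or procedure-related eye reports in all arms, which the early review would have to read with care. The plan already departs from purely non-leading questioning for four symptoms, so the change extends an approach it has adopted.
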